## Participants

We recruited participants, aged 8-17 years, with ASD from the psychiatry outpatient clinic of CGMH, Linkou, Taiwan. DSM-IV autistic disorder or Asperger's

disorder, or DSM-5 ASD was clinically diagnosed and corroborated using the Autism Diagnosis Objective Schedule (Lord et al., 2000). Exclusion criteria included: FIQ<70 based on the Wechsler Intelligence Scale for Children-3rd or Wechsler Adult Intelligence Scale-3rd (a cutoff at 16 years), any prior history of major neurological (especially epilepsy) or medical illness, mood and anxiety disorders, schizophrenia and substance misuse. Participants with co-occurring attention-deficit hyperactivity disorder (ADHD) were included, and assessed by experienced child psychiatrist ([name], [name], [name]). Since there are high psychiatric comorbidities in ASD (70% at least one comorbidity), we intended to design the current protocol to strike a balance between the generalizability, feasibility, as well as the heterogeneity resulted from the psychiatric comorbidities. Therefore, we decided to include those comorbid with ADHD, which is the most common co-occurring condition, has similar neurodevelopmental nature, and might share some etiologies with ASD, but exclude people with the co-occurring conditions which may happen in association with ASD but are not inherent in neurodevelopmental conditions (i.e., these disorders happen chronologically after ASD). Simultaneously, the effect of iTBS over the pSTS on other major psychiatric disorders are unknown, but is well tolerated in people with co-occurring ADHD (Ni et al., 2017). To minimize potential harms and heterogeneity, people with co-occurring mood and anxiety disorders, schizophrenia and substance misuse were thus excluded from the current trial. All psychotropic medications were continued without change during the trial. All participants had been naïve to any non-invasive brain stimulation treatment.

### **Intervention**

A 70-mm figure-of-eight coil connected to a Magstim Super Rapid system (Magstim Company, Oxford, UK) was used. Initially, the coil was placed tangentially to the scalp over the contralateral motor cortex with the handle pointing backward. The location of motor “hot-spot” was determined where single-pulse TMS produced the largest motor evoked potentials (MEPs) from the FDI at rest. We measured the active motor threshold (AMT) as the minimum stimulation intensity needed to elicit MEPs of no less than 200 uV in 5 out of 10 trials during 20% of maximum voluntary contraction of the FDI.

This study administered the iTBS protocol (Huang et al., 2005) as follows: Each TBS train was comprised of a burst of 3 TMS pulses at 50 Hz, at 200 ms intervals, for 10 times. The TBS train was delivered every 10 seconds for 20 times to have 600 pulses in total for each iTBS course. In each iTBS session, we first delivered two iTBS with a 3-minute break over the left pSTS. 5 minutes later, we then delivered the other two iTBS over the right pSTS. The intervention pulses in each session were 1200 for each

hemisphere (in total 2400 pulses/session; 38400 pulses/study). The stimulus intensity of iTBS over the pSTS was 80% of AMT for the active intervention, but 60% AMT for the sham intervention. The sham stimulation was still targeted on the bilateral pSTS, but delivered with the coil tilted one-wing 90° off the head (Lisanby, Gutman, Luber, Schroeder, & Sackeim, 2001), which is a valid sham condition commonly used in double- or single-blind sham-controlled RCT across major psychiatric disorders (Lefaucheur et al., 2020). This one-wing 90° tilted coil sham manipulation is devoid of detectable biological effects (Lisanby et al., 2001) and produces haptic and auditory simulation. No any participant assigned in the Sham group at Phase 1 actively disclosed or guessed that he or she received the sham stimulation.

The location of the bilateral pSTS was defined based on the meta-analysis of functional MRI (Van Overwalle & Baetens, 2009). These regions were registered to each individual's native structural image in the Navigated Brain Stimulation system (Nexstim®, Helsinki, Finland). The details of localization process are reported elsewhere (Ni et al., 2017). Whether the lateralization exist in function of the pSTS remains elusive. Unlike the target site selection in depression, one recent study demonstrated 18 sessions of rTMS applied over bilateral DLPFC produces the most striking positive effects on improving symptoms in children and adolescence with ASD (E. M. Sokhadze et al., 2018). Furthermore, our prior preliminary study also shows the potential therapeutic effects of bilateral pSTS stimulation in adults with ASD (Ni et al., 2017). We thus followed this principle to set the target site at the bilateral pSTS.

## Outcomes

The primary outcomes included the safety profiles, as well as the social deficits as measured by the caregiver-rated Social Responsiveness Scale (SRS) (Gau, 2013), since theoretically targeting the pSTS is aimed to modulate the activity within the social brain network. Atypical social cognition is often associated with the autistic symptoms. The secondary outcomes thus included two common tasks assessing the social cognition performances of people with ASD (Barahona-Correa et al., 2018), i.e., the Reading the Mind in the Eyes test (RMET) (Baron-Cohen, Wheelwright, Hill, Raste, & Plumb, 2001; T. S. Li et al., 2020) and Frith-Happe Animations Task (White, Coniston, Rogers, & Frith, 2011) (Barch et al., 2013). Notably, these two tasks, nonetheless, are not specific to the pSTS activities. Given our preliminary beneficial results in compulsory behaviors in adults (Ni et al., 2017), we also adopted the Repetitive Behavior Scale-Revised (RBS-R) (Bodfish, Symons, Parker, & Lewis, 2000; Y. C. Yang et al., 2019) as the exploratory outcome. Higher scores on the SRS and RBS-R represent greater severity of the two domains of autistic symptoms. RMET total scores represent how many correct mental states the participant has inferred from the eyes, indicating

individual's theory of mind capability. Frith-Happe Animations also tap mentalizing capacity by asking the participant to infer whether interaction intents exist between two triangles. When the participant answered about the presence/absence of interactions, he/she was further asked to select words that best described how these triangles were feeling at the end of each video clip. Participants scored 1 point for correct answers to either presence/absence or exact description of mental states, which are summarized as the total Categorical scores and Feelings scores, respectively. To enhance a contrast and reduce assessment time, we adopted the revised Frith-Happe Animations following those used in the Human Connectome Project (Barch et al., 2013), which only included social and random interactions.

Side effects were assessed immediately after each session and at one-month follow-up using open-ended questions inquiring any physical discomfort and then close-ended questions including "pain at application site", "headache/dizziness", "tinnitus" and "anxiety" experienced during and after iTBS

### Statistics

Herein we only reported clinical and cognitive data during RCT. Independent t-test and chi-square test were used to evaluate the difference of baseline characteristics. To simultaneously examine the immediate effect of pSTS vs. sham stimulation in different visits, the generalized estimating equations (GEE) model was conducted using the data of Baseline, Week 4, and Week 8. To account for correlations between individuals' repeated measurements between visits, a working correlation matrix with a first-order autocorrelation was used with the robust estimator of standard error. Treatment, Time, and a two-way interaction (Active vs. Sham  $\times$  Time) effects were modeled in the GEE. The maximum likelihood method in the GEE was used to address the missing values from dropouts. In consideration of high inter-individual variability in the clinical symptoms and social cognitive function at baseline, we also implemented an additional analysis using the symmetrized percentage change (Ayers, 2006) to investigate the iTBS effects. Because there was significant difference for both groups at baseline in the RMET, all of the analyses in the GEE and symmetrized percentage change were adjusted.

To comprehensively examine effects across time for both conditions, exploratory within-group comparisons were also conducted in the same GEE regardless of whether the main effect was statistically significant. However, when the main effect of GEE is not statistically significant, the significant findings in these exploratory within-group comparisons should be interpreted conservatively. The correction for multiple comparisons was implemented to avoid type-I errors. Five pairwise within-group comparisons (i.e., Baseline vs. Week 4, Baseline vs. Week 8, Baseline vs. Week 12,

Week 4 vs. Week 8, Week 8 vs. Week 12) were calculated separately in Active (8-week active TBS) and Sham (4-week sham followed by 4-week active TBS) groups.

Considering clinical heterogeneity in ASD, we defined responders based on the Reliable Change Index (RCI) calculated using the SRS total scores. The RCI takes into consideration the false positive outcome that could occur due to random error from repeated measurements alone (Jacobson & Truax, 1991). The RCI represents differences in individual's scores between before- and after-intervention, divided by the standard error of the difference of the measure. Responders were those with RCI  $>1.64$ , which corresponds to  $p<0.05$  with one-sided test (i.e., the null hypothesis was that iTBS would not help with social symptoms). Demographic and clinical features were compared between the responders and non-responders using non-parametric tests.

In addition to the stratified analysis based on responsiveness, we also tested a three-way interaction (Active vs. Sham  $\times$  Time  $\times$  Modifier) to explore whether iTBS over the pSTS is more beneficial for individuals with ASD with certain characteristics. Effect modifiers included demographics, intelligence quotient, clinical traits, comorbidity, and medication.

Statistical analysis was performed using the SAS Version 9.4 software (SAS Institute, Cary, NC, USA). Considering multiple comparisons including the clinical symptoms and social cognitive function (5 measurements), the GEE, within-group analyses and three-way interaction were considered statistically significant at  $p\text{-value}\leq0.01$ . Despite contention, herein, alpha level in-between 0.01 and 0.05 were considered a nominal significance for hypothesis generating for the future study (Bays, 2019).

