**【 2020/12/14 】**

## Design

This was a 4-week randomized, parallel, single-blind and sham-controlled trial, followed by another 4-week open-label intervention, to investigate the feasibility and efficacy of iTBS over the bilateral pSTS in children and adolescents with ASD at Chang Gung Memorial Hospital (CGMH, Linkou, Taiwan). There were 2 phases in this RCT, with one-month follow-up. Specifically, after baseline assessments, participants were randomized to the Active or Sham group (Phase 1, Baseline-Week 4). Given limited human resources, the investigator ([name]) and his assistant assessed and delivered rTMS to all participants. Therefore, only participants and their caregivers were blind to the treatment condition (single-blind). Active versus sham iTBS was administered over the pSTS 2 days/week for 4 weeks. Entering Phase 2 (Week 5-8), participants were unblinded, and then active iTBS over the pSTS were administered to all participants 2 days/week for the other 4 weeks. This distinct design allowed for a conventional rigorous RCT of low risk of bias (Phase 1), and concomitantly resolved a potential inequity issue by providing access to iTBS for every participant (Phase 2) (Green, 2008). This also enabled investigating effects of longer treatment courses. Considering the feasibility based on their school activities, participants freely chose 2 intervention days, which are at least 48 hours apart from each other, from Monday to Saturday in the beginning of their interventions. Once they made the choice, the schedule of sessions was fixed throughout the trial.

Clinical assessments were completed in participants within one week of the first iTBS session of Phase 1 (Baseline) and Phase 2 (Week 5), following the last iTBS session (Week 8), as well as at follow-up (Week 12). With the same baseline and follow-up assessment schedule, social cognition was specifically measured within 1 hour following the last iTBS session of Phase 1 and 2, respectively.

A minimum total sample size of 68 was estimated using G\*Power 3.1 (Faul, Erdfelder, Buchner, & Lang, 2009), being powered (90% power and two-sided 5% significance) to detect a standardized effect at 0.4 from within-between interaction of the repeated-measure ANOVA model. The estimated effect size was guided using the pool effect on social behavior deficits in existing studies (Barahona-Correa et al., 2018).

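### The active-versus-sham GEE includes the unblinded, all-active Week 8 visit, and no section names the visit or contrast that decides SRS efficacy

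*Combined protocol and SAP*

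**What the plan says.** **Design.** Randomised sham control belongs to Phase 1, which is described as "a conventional rigorous RCT of low risk of bias (Phase 1". On entry to Phase 2, "participants were unblinded, and then active iTBS over the pSTS were administered to all participants 2 days/week for the other 4 weeks". The design gives a reason for following both arms further: "This also enabled investigating effects of longer treatment courses". The total of 68 is sized on the group-by-time interaction of a repeated-measures ANOVA. The number of visits and the correlation are not stated.

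**Outcomes.** The primary outcomes are safety and "the social deficits as measured by the caregiver-rated Social Responsiveness Scale (SRS". No time point is attached to the SRS.

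**Statistics.** The aim of the model is given as "To simultaneously examine the immediate effect of pSTS vs. sham stimulation in different visits". For this, "the generalized estimating equations (GEE) model was conducted using the data of Baseline, Week 4, and Week 8", with Treatment, Time and their interaction as terms. A significance limit of p ≤ 0.01 is set for the GEE as a whole. Baseline to Week 4 is named only in a list of five exploratory comparisons inside each arm. These are said to come from the same GEE, and two of them use Week 12.

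**Assessment timing (Design).** "Clinical assessments were completed in participants within one week of the first iTBS session of Phase 1 (Baseline) and Phase 2 (Week 5"), then at Weeks 8 and 12. By contrast, "social cognition was specifically measured within 1 hour following the last iTBS session of Phase 1 and 2".

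**The concern.** A test of active against sham should rest on the period in which one arm received sham and the families did not know the allocation. That period ends before Phase 2. By Week 8, at two sessions a week, the arms have had 2 × 8 = 16 and 2 × 4 = 8 active sessions. Their difference measures a longer against a shorter (and later) active course, observed without blinding.

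A three-visit interaction pools this difference with the Week 4 difference. Because the plan does not say which part of the GEE decides the SRS, a result driven by the open-label phase could be reported as evidence against sham. The p ≤ 0.01 limit does not prevent this, because it is not tied to a term or a visit. The modifier analysis, with its three-way interaction, is exploratory and does not supply the missing contrast.

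**Working it through.** **1. The plan's own figure.** Take two groups, m = 2 measurements and correlation 0.5, with the stated 0.4 read as a standardised mean difference, so f = 0.2 (all assumed except the 0.4 and two groups). The noncentrality is λ = f²·N·m/(1 − ρ) = 0.04 × 68 × 2/0.5 = 10.88. With 1 and 66 df at two-sided 0.05, power is 0.9015, so 68 is reproduced. With m = 3, the number of visits in the GEE, the same formula gives 56 at correlation 0.5; it gives about 68 only near correlation 0.38. This suggests sizing on one post-baseline visit but does not prove it.

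**2. Set-up of the illustration.** From the plan: 68 participants and alpha 0.01. Assumed: 34 per arm, no dropout, SD 1 at each visit, correlation 0.5, categorical time, normal approximation. Let δ hold the between-arm differences in change from Baseline at Week 4 and Week 8, and let V be their covariance, which carries the factor 2/34 = 1/17. The 2-df interaction has λ = δ′V⁻¹δ and critical value 9.21. The 1-df Week 4 contrast has critical value 6.63.

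- AR(1), the plan's working correlation: the changes have variances 1 and 1.5 and covariance 0.75, so the determinant is 1.5 − 0.5625 = 0.9375.
- Compound symmetry (CS): variances 1 and 1, covariance 0.5, determinant 0.75.

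**3. No Week 4 effect, difference at Week 8 only.**

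| Week 8 difference | λ, AR(1) | 2-df rejects, AR(1) | λ, CS | 2-df rejects, CS | Week 4 contrast rejects |
|---|---|---|---|---|---|
| 0.2 SD | 0.04 × 17/0.9375 = 0.73 | 3.1% | 0.04 × 17/0.75 = 0.91 | 3.7% | 1.0% |
| 0.4 SD | 0.16 × 17/0.9375 = 2.90 | 13.4% | 0.16 × 17/0.75 = 3.63 | 17.9% | 1.0% |

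For 0.4 SD with correlations of 0.3 to 0.7, the range is 10% to 25% under AR(1) and 12% to 35% under CS.

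**4. Check by simulation.** In 20,000 trials per setting with the robust variance, correlation 0.5 and 0.4 SD at Week 8, the 2-df test rejected in 15.9% (AR(1)) and 20.7% (CS), and the Week 4 contrast in 1.2% to 1.5%. Of the 2-df rejections, 83% to 85% had a Week 4 p-value above 0.05. With no difference at any visit the 2-df test rejected in 1.7% to 1.8%, so a small part of the excess over the analytic figures comes from the robust variance at this sample size.

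**5. Price of the 1-df test.** Take a true 0.4 SD effect at Week 4 and full catch-up by the sham arm at Week 8 (AR(1), correlation 0.5, alpha 0.01). The 2-df test has λ = 0.16 × 17 × 1.5/0.9375 = 4.35 and power 23%. The Week 4 contrast has λ = 0.16 × 17 = 2.72 and power 18%. Under half catch-up (0.2 SD left at Week 8) the 2-df test has 13%, and the Week 4 contrast still has 18%.

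**6. Visits the model cannot supply.** The listed GEE data are Baseline, Week 4 and Week 8. Baseline to Week 12 and Week 8 to Week 12 are two of the five comparisons inside each arm, and neither can come from those data.

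**The case against.** The strongest reply is that the plan already contains the right result. The sample size is built on a group-by-time interaction, so Treatment × Time is the natural efficacy term. The stated aim refers to effects at different visits, and the visit-to-visit comparisons imply categorical time, so a Treatment × Week 4 coefficient is very probably fitted. The Week 8 data are included openly and for a stated reason. On this view the defect is one of labelling, and the 13% to 18% arises only if an omnibus 2-df test is read, which no section mentions. Most of this stands and limits the point. It does not close the gap, because neither the sizing statement nor the aim says which visit, or how many degrees of freedom, decides the SRS.

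A reader might infer more than the documents support:

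- *That the Treatment effect averaged over visits is the efficacy result.* The undefined main effect of the GEE governs only how cautiously the comparisons inside each arm are read. The sizing basis favours the interaction.
- *That caregivers knew the allocation when rating the SRS at Week 8.* This is likely, since Phase 2 is open-label and participants were unblinded, but the text does not say it of caregivers.
- *That every Week 8 rejection is a false positive.* Sixteen against eight active sessions is a real difference between randomised arms. The error would lie in calling it active against sham.
- *That the Week 4 contrast is certainly blinded.* The SRS is placed at Week 5 in the Design section and analysed as Week 4. The parallel wording for Baseline suggests that it preceded the first Phase 2 session, but its order relative to unblinding is not stated.

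**Conclusion.** The point holds as an omission: the plan does not name the visit or contrast that decides SRS efficacy, and the model offered for the sham comparison includes a visit at which no arm is on sham. That much is plain from the text.

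The size of the consequence is conditional. It needs the three-visit interaction to be the result read, and a difference that appears only in Phase 2; the documents establish neither. On those assumptions the chance of a significant active-versus-sham result is modest for a 0.4 SD difference and small for 0.2 SD, and it rises with the correlation between visits. It is not a type I error rate, because the arms do differ at Week 8 in that scenario.

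The missing Week 12 data and the Week 5/Week 4 mismatch are separate inconsistencies in the same part of the plan. They need correction but do not make the main point more serious. The point should be fixed; it does not invalidate the trial, since the contrast needed can be obtained from data already collected.

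**What to change.** 1. State that time is categorical, and make the 1-df Treatment × Time contrast for Baseline to Week 4 the deciding efficacy test for the SRS. Label it post hoc if it is set after the data were seen.
2. Report the Week 8 between-group result as open-label and exploratory, under its true description: 8 weeks active against 4 weeks sham then 4 weeks active.
3. Replace the reference to the main effect of the GEE with the named term.
4. Fit the comparisons inside each arm in a model that includes Week 12.
5. Reconcile Week 5 (Design) with Week 4 (Statistics) for the SRS, and state whether it was rated before unblinding. If it was not, say that the Week 4 contrast is not blinded.

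**Cost.** One contrast statement, one refit, and a check of SRS rating dates against unblinding dates; no new data. Week 8 leaves the confirmatory claim. The 1-df test gives up some power under full sham catch-up, and at 0.4 SD and alpha 0.01 its power is low in any case (step 5). The document is retrospective, since it already reports an observed baseline difference in the RMET, so a contrast named now carries less weight than a prespecified one.

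### The plan credits maximum likelihood with handling dropouts, but the GEE it describes has no likelihood, so general validity under missing at random is not provided

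*Combined protocol and SAP*

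**What the plan says.** All of this is in the Combined protocol and SAP.

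- Statistics, on the model: "the generalized estimating equations (GEE) model was conducted using the data of Baseline, Week 4, and Week 8", and "a working correlation matrix with a first-order autocorrelation was used with the robust estimator of standard error". The terms are Treatment, Time and their interaction.
- Statistics, on missing data: "The maximum likelihood method in the GEE was used to address the missing values from dropouts". This is the only statement on missing data. The document gives no missingness assumption, weighting, imputation, missing-data sensitivity analysis or dropout rate. SAS 9.4 is named, but no procedure.
- Statistics, on adjustment: "all of the analyses in the GEE and symmetrized percentage change were adjusted", prompted by a baseline difference in the Reading the Mind in the Eyes test. The form of the adjustment is not given.
- Statistics, on within-group changes: "exploratory within-group comparisons were also conducted in the same GEE". The list opens "Five pairwise within-group comparisons (i.e., Baseline vs. Week 4, Baseline vs. Week 8, Baseline vs. Week 12" and continues with Week 4 against Week 8 and Week 8 against Week 12.
- Design, on timing: "Clinical assessments were completed in participants within one week of the first iTBS session of Phase 1 (Baseline) and Phase 2 (Week 5". In Phase 2, "active iTBS over the pSTS were administered to all participants".

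**The concern.** Someone who reads that maximum likelihood dealt with dropouts will normally take the estimates to be valid under missing at random, that is, when dropout depends on scores already observed. A GEE with a working correlation does not have that property in general. The robust standard error does not supply it either: it corrects the stated precision when the working correlation is wrong, but not bias in the estimate.

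The SRS is the primary efficacy outcome, and this sentence is the only account of how its missing values were treated. The reader therefore cannot tell which assumption the result rests on. The comparison of active with sham is at the visit that the GEE calls Week 4 (for the SRS, the assessment around the first Phase 2 session). Week 8 enters the same Treatment by Time test, although both arms receive active stimulation by then. Within-group changes are exposed in a further way: bias common to both arms cancels between arms but stays within each arm.

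**Working it through.** **1. What the equations do.** The GEE solves Σ D′V⁻¹(Y − μ) = 0 with V = φR(α), where R is AR(1) and φ is one common variance. Gaussian maximum likelihood has the same form, but with V a covariance estimated by likelihood. With dropout, the GEE in effect predicts a missing score from the observed ones using its working covariance. Take a true correlation of 0.7:

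- Lost after Baseline: AR(1) predicts Week 4 with slope α. The true slope is 0.7 with equal SDs, and 0.7 × 1.3 = 0.91 if the Week 4 SD is 1.3 times the baseline SD.
- Lost after Week 4: AR(1) predicts Week 8 from Week 4 alone. If the truth is exchangeable with equal SDs, the slopes are 0.7/(1 + 0.7) = 0.41 on each of Baseline and Week 4. If the truth is AR(1) with constant variance, they are 0 and 0.7, which is the form the GEE uses.
- The moment estimate of α is itself taken from the remaining participants. It came out at 0.62 to 0.65 in large-sample runs with opposite selection, so a small bias remains even when AR(1) is true.

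**2. Inputs.** From the documents: the three visits, AR(1), the Treatment by Time contrast, and a total of 68, hence 34 per arm. The plan gives no figure on missing data to reproduce. Its 68 does reproduce as the G*Power within-between interaction with f = 0.2 (d = 0.4), two visits and ρ = 0.5 (these settings are my assumptions): λ = f²Nm/(1 − ρ) = 0.04 × 68 × 2/0.5 = 10.88, power 0.9015.

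Assumed, because the documents are silent: no true effect; 16% lost by Week 4 and 27% by Week 8; log-odds of dropout 1.5 per SD of the last observed score; correlation 0.7; SDs either equal or rising (1, 1.3, 1.4).

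**3. Absolute bias of the three-visit GEE, in baseline SDs.** Ranges run from selection in one arm only to opposite selection in the two arms.

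| True covariance and selection | Contrast | Week 4 | Week 8 |
|---|---|---|---|
| Exchangeable, equal SDs | between arms | 0.00–0.02 | 0.04–0.12 |
| Exchangeable, rising SDs | between arms | 0.04–0.10 | 0.10–0.23 |
| AR(1), constant variance | between arms | at most about 0.02 | at most about 0.05 |
| Same selection in both arms | between arms | about 0 | about 0 |
| Exchangeable, equal SDs, same selection | within arm | 0.01 | 0.06 |
| Exchangeable, rising SDs, same selection | within arm | 0.05 | 0.12 |

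Separately coded runs of this set-up agree within about 0.03 SD. For scale, with 34 per arm the standard error between arms is 0.20–0.25 at Week 4 and 0.22–0.30 at Week 8. For change within an arm it is 0.15–0.18 and 0.16–0.21.

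**4. Variations.**

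- Loss of 5%/10%, exchangeable truth: 0.00 and 0.02–0.03 (equal SDs); 0.01–0.03 and 0.03–0.08 (rising).
- Adjusting for a baseline covariate (assumed correlation 0.3 with the baseline score, arms 0.5 SD apart), opposite selection, 16%/27%: 0.02 and 0.09 (equal), 0.08 and 0.20 (rising), against 0.02 and 0.11, 0.09 and 0.21 unadjusted in the same runs. Adjustment of this kind does not remove the bias.
- Maximum likelihood with unstructured covariance stayed within 0.006 SD in every missing-at-random case.
- Dropout driven by the unseen current score, opposite selection, 16%/27%: the GEE is biased by 0.21 and 0.32 (equal) or 0.31 and 0.49 (rising), and maximum likelihood by 0.21 and 0.24 or 0.27 and 0.34.

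**5. Week 12, a separate matter of reading.** The GEE is stated for Baseline, Week 4 and Week 8. Two of the five comparisons said to come from it (Baseline against Week 12, Week 8 against Week 12) use a visit outside that set.

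**The case against.** The case for leaving the sentence alone has real substance.

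- **The gap may be small.** For a continuous outcome, the GEE nearly coincides with Gaussian likelihood when its working covariance is right. A reader might infer that protection against informative dropout is wholly absent. The documents do not support that: if AR(1) with constant variance holds, the bias is at most about 0.05 SD. The plan also never mentions missing at random; that is what a reader takes from the words maximum likelihood.
- **The sham comparison is barely touched.** Only Week 4 compares active with sham, and the bias there is 0.00–0.02 SD with equal SDs and at most about 0.10 with rising SDs, against a standard error of 0.20–0.25.
- **The larger figures stack assumptions.** They need an odds ratio of about 4.5 per SD (e^1.5), opposite selection by arm, SDs 30–40% larger than at baseline, 27% loss and a correlation that is not AR(1). With AR(1) and rising SDs, Week 8 bias is 0.05–0.14 rather than 0.10–0.23. A reader might infer that the SRS result is biased. With no dropout rate, direction or SDs in the documents, that cannot be said.
- **A mixed model is not the only remedy**, and step 4 shows that it is no cure when dropout depends on unseen scores.
- **Week 12** may simply mean the same specification extended by one visit.

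All of this limits the size of the problem and the strength of the remedy. None of it makes the sentence correct. If the words refer to likelihood-based starting values in the software, those give no missing-at-random validity either.

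**Conclusion.** The point holds as an error in the stated method. The plan attributes its handling of dropouts to a likelihood that the described GEE does not have, and it gives no missingness assumption in its place. General validity under missing at random is not provided by this method. What it does offer is validity when data are missing completely at random or missingness depends only on modelled covariates, and approximate validity when AR(1) with constant variance is right.

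The effect on the trial's results is unknown. Under the assumed inputs it is small for the active-versus-sham contrast at Week 4. It is larger at Week 8 if the correlation is not AR(1), and about zero between arms if selection is alike in both. In that last case the within-group changes are still biased. These sizes rest wholly on the assumed loss, selection and covariance, and do not show that any reported estimate is wrong.

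**What to change.** 1. Replace the sentence with what was actually run. If that was a GEE on all available visits without weighting or imputation, say so. Add that it is valid if data are missing completely at random or missingness depends only on modelled covariates, and approximately valid if AR(1) with constant variance is right.
2. Keep the specified GEE as the main analysis. For the SRS, add a likelihood-based mixed model for repeated measures in SAS 9.4 (REML, unstructured covariance, same fixed effects and adjustment). Label it a post hoc sensitivity analysis, since the text describes the analysis as already done. State that it is valid under missing at random but not if dropout depends on the unseen score. A weighted GEE, or multiple imputation before the GEE, is an acceptable alternative that keeps the specified estimator.
3. Report dropout by arm and visit.
4. As a separate clarification, state which model gave the two Week 12 comparisons.

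The cost is one corrected sentence, a short table and one SRS model for Treatment by Time, plus a second, four-visit fit if the within-group comparisons are also checked. The mixed model estimates more covariance parameters: 3 × 4/2 = 6 for three visits or 4 × 5/2 = 10 for four, against 2 for the GEE.
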